7. STUDY-WIDE NUMBER OF SUBJECTS*

N/A

8. STUDY-WIDE RECRUITMENT METHODS*

N/A

9. STUDY TIMELINES*

Describe:

- *The duration of an individual subject's participation in the study:* 6 months
- *The duration anticipated to enroll all study subjects:* 1.5 years
- *The estimated date for the investigators to complete this study (complete primary analyses):* 3 years

10. STUDY ENDPOINTS*

Please see below table describing the primary and secondary outcome measures

SN=School Nurse

MP=Medical Provider

AC=Asthma Champion

Study Assessments, Measures and Data Collection Timing

Variable	Measure/Instrument
Designed for and Delivered to pediatric practice staff, school staff, and parent-child dyads Administered by Research coordinator	
AIM 1: Primary Feasibility Outcomes for Asthma Link™ research protocol (cluster RCT)	

INVESTIGATOR STUDY PLAN

Participation/Recruitment	# of screened and eligible participants; # refusing to participate; reason(s) for refusal
Retention	# of dropouts; subjects lost to follow-up; reason(s) for dropping out
Program usage/Intervention Fidelity (degree to which using program)	
 Checklist for pediatric practice staff to assess % of eligible children enrolled (see Pedi Practice checklist) School nurse report of % enrolled students receiving supervised therapy (see SN checklist) School nurse checklist of each enrolled child attending daily school nurse sessions and his/her family bringing medicine to school (see SN checklist)
AIM 1: Secondary Asthma Health Outcomes	
Asthma symptoms	
 Asthma Control Test (see Parent surveys), validated maximum symptom days, validated
ED visits, Admissions, Oral steroids, Medication Adherence	
 Parent report (see Parent surveys) and electronic medical record review Pharmacy refill data
Spirometry	
 Portable Spirometer (PIKO), validated⁵⁷ to assess Forced Expiratory Volume in 1sec
School absences	
 Parent and school nurse report (see Parent surveys and SN checklist)
AIM 2: Process Outcomes for Asthma Link™ Intervention Protocol	
Acceptability	
 Acceptability rating scale (5 point Likert scale) to rate each component of the Asthma Link™ intervention (see Parent, SN, MP, AC surveys)
Adoption	
 Pedi practice log to track number of providers offering Asthma Link™ (See Pedi Practice Intervention Fidelity Checklist) School nurse log to track frequency of child coming to nurses office to receive med (see SN checklist) School nurse log to track family bringing in medicine to school (see SN checklist) Survey to family to assess ability to obtain 2 inhalers (one for home and one for school) and deliver medicine to school (see Parent 3 mo, 6mo survey)
Costs	
 Survey to assess time and costs for: pediatric practice to train in and implement program, School nurse to deliver intervention, Family to pick up medicine and bring to school (transportation), above and beyond their daily routines (see MP, AC, SN, Parent surveys)
Sustainability	Brief Sustainability Rating (5 point Likert scale) to assess pediatric practice, School nurses, and Families perception that Asthma Link™ could be continued over time (see MP, AC, SN, Parent surveys)

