In response to this critical public health issue, we propose to study Asthma Link, which is a low-cost, low-intensity community-clinical based model of supervised asthma therapy in schools. Asthma Link is an established, ongoing clinical program that promotes the adoption of the evidenced-based practice of school-supervised asthma therapy in real world settings.

Asthma Link connects the three groups that play vital roles in the health of school-aged children with asthma: pediatric practices, school nurses, and families. Pediatricians identify and enroll children with poorly controlled asthma and medication non-adherence as part of their routine practice. They send the school nurse an order for daily, supervised inhaled steroid administration at school. Families bring the prescribed inhaler to school. The school nurse supervises the child's inhaler administration and provides adherence education, as part of her daily routine, to ensure adherence and proper inhaler/spacer technique. Ongoing communication occurs between the pediatric practice, the school nurse and families throughout the school year. Asthma Link is based on prior research studies that demonstrate the safety and efficacy of school-supervised asthma therapy. The goal of Asthma Link is for school-supervised asthma therapy to operate in a real-world setting, delivered by pediatricians, school nurses and families within their current routines and relying on minimal resources and no research staff.

The goal of the proposed study is to examine the effectiveness and implementation of Asthma LinkTM in sustainable real-world practice.

Preliminary Data:

The current proposed study builds from our prior research, which has informed the proposed study. To initially test Asthma LinkTM, we performed a small pre/post study (SEE IRB DOCKET # H00010546_2) of 84 children enrolled in Asthma LinkTM (mean age 10 years, 95% Medicaid insurance, 67% Latino, 19% Black). We observed that children enrolled in Asthma LinkTM experienced a 54% decline in emergency room visits, a 95% decline in hospital admissions and a 46% decline in rescue medication use over a one-year follow-up period ($p<0.001$),¹⁷ demonstrating that Asthma LinkTM merits further rigorous evaluation. Additionally, in order to examine the barriers and facilitators to Asthma LinkTM real-world implementation, (SEE IRB DOCKET # H00012920_1), we are interviewing program stakeholders which include school

INVESTIGATOR STUDY PLAN

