nurses, parent-child dyads, and medical providers who were participating in the program in addition to public health and insurance officials. Specifically, in our interviews with 12 school nurses, we found that they perceive Asthma Link™ to be an acceptable program given the brief (<5min) time required and ease of incorporation into their existing routine.

Despite our promising results, Asthma Link™ needs to be tested against a comparison group, using a cluster randomized controlled trial (RCT). The first step is to perform a pilot cluster RCT to assess feasibility outcomes and health outcomes (Aim 2). Additionally, it is imperative to assess process outcomes (acceptability, adoption, costs, sustainability) of Asthma Link™ in new pediatric practices to ensure that school-supervised asthma therapy can be successfully scaled up and utilized in real world practice (Aim 1). We propose to test Asthma Link™ using a pilot cluster RCT of 4 pediatric primary care sites in Massachusetts.

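### The Costs outcome does not say which daily routine extra time is counted against, so school-nurse delivery time could be recorded as little or nothing

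*Combined protocol and SAP*

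**What the plan says.** Section 4 (Objectives) names costs as one of four process outcomes, with acceptability, adoption and sustainability. The Costs row in section 10 (Study Endpoints) defines the measure. It opens with "Survey to assess time and costs for: pediatric practice to train in and implement program" and continues with "School nurse to deliver intervention, Family to pick up medicine and bring to school (transportation), above and beyond their daily routines". The row refers to the medical provider, Asthma Champion, school nurse and parent surveys for the items.

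Section 5 (Background) describes the work being costed. The school nurse supervises the inhaler and "provides adherence education, as part of her daily routine, to ensure adherence and proper inhaler/spacer technique". The stated goal is supervised therapy "delivered by pediatricians, school nurses and families within their current routines and relying on minimal resources and no research staff". Under Preliminary Data, 12 interviewed school nurses found the programme acceptable "given the brief (<5min) time required and ease of incorporation into their existing routine".

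Section 11 (Procedures Involved) lists cost as a construct in the school nurse, provider and Asthma Champion surveys, given at baseline and end of intervention, and in the follow-up parent surveys for the Asthma Link condition. The wording of the items is not reproduced. Section 13 gives no costing method, and no section gives a unit cost, a wage rate or a costing perspective.

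**The concern.** The cost measure is incremental, and an incremental measure needs a stated baseline. Here the baseline is a routine, and the plan elsewhere describes programme delivery as belonging to the routine. A nurse who has taken the daily supervised dose into her working day, as the programme intends, can reasonably read the question as asking only for what lies outside that day. Another nurse doing the same work can reasonably count all of it.

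Two things are at stake. First, the first reading biases cost downward, and more so where integration is better. Section 5 presents Asthma Link as low-cost and attributes the poor uptake of earlier school programmes largely to expense and resource demands, so the bias runs toward the claim that this outcome examines. Second, answers would vary with each respondent's understanding of the qualifier and would be hard to compare across nurses, practices and families. Respondents, not analysts, apply the qualifier. Minutes that a nurse leaves out cannot be restored in analysis.

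**Working it through.** The plan states no cost figure, so there is nothing to reproduce. The check is a comparison of wording, followed by an illustration of scale.

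**Wording**

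| Place | What it does |
|---|---|
| Section 10, Costs row | Lists nurse delivery as an item to be costed, then closes the list with a qualifier limiting the count to what exceeds the daily routine |
| Section 5, programme description | Places the nurse's supervision and education in her daily routine |
| Section 5, programme goal | Aims for delivery by pediatricians, nurses and families inside current routines |
| Section 5, Preliminary Data | Reports a short nurse time and easy fit with the existing routine |

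Two readings are open:

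- **A. The routine is the one without Asthma Link.** Supervised sessions are extra, and all the time spent on them counts.
- **B. The routine is the one now followed, with Asthma Link in it.** Supervised sessions are inside the baseline, and little or none of the time counts.

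Nothing in the documents chooses between them. Wording that referred only to the period before the study would not settle the matter either. Section 5 calls Asthma Link an established, ongoing clinical programme, section 11 says families were recruited to it from the Worcester community for the earlier pre/post study, and section 22 places the four study practices in Worcester. Some nurses may already supervise doses for other children. The documents do not say how many.

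**Scale (illustrative)**

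Inputs from the documents:

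- Supervised administration at school is daily (section 5).
- Nurse time is under 5 minutes, with no unit stated (section 5).
- There are 36 dyads per condition (section 13).

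Assumed inputs: 90 to 180 school days attended, and 1 to 5 minutes per session.

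Formula: nurse-hours per child = days × minutes per session / 60.

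- Low: 90 × 1 / 60 = 1.5 h per child, and 1.5 × 36 = 54 h per condition.
- High: 180 × 5 / 60 = 15 h per child, and 15 × 36 = 540 h per condition.
- Reading B, fully applied: 0 h.

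The same work could thus be recorded as 0 h, or as a value between 1.5 and 15 h per child, depending only on how the respondent reads the qualifier. The high figure is an upper bound. It takes the limit of the reported time as a per-session value and assumes attendance every day of a full school year.

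**The case against.** The strongest reply is that the ordinary sense of the qualifier is incremental: it asks what the programme adds. The same row expressly lists nurse delivery as something to be costed, and reading B would empty that item. This stands in part. A reader might infer that the rule, taken literally, forces nurse time to zero. The documents do not support that. Zero is one reasonable reading and reading A is another. The qualifier might even attach grammatically only to the family item, although its plural possessive closes a list of three parties.

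The section 5 text describes how the programme runs and is not a costing rule, and delivery by all three groups within current routines is stated as a goal, not a definition. That is fair. It does not remove the conflict, because respondents are asked about a routine that the programme aims to become part of.

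The interviewed nurses apparently recognised a positive time while also finding the work easy to absorb, which suggests that nurses can report time they regard as routine. This is relevant evidence, but it comes from interviews, not from a survey carrying this qualifier.

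The uploaded survey items may already ask for minutes per session. That cannot be checked here, so the point is conditional for the surveys. It is not conditional for the outcome definition in section 10.

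Finally, costs are a descriptive outcome in a pilot. The plan sets no cost threshold and no between-arm cost comparison, section 13 does not use cost in planning the larger trial's sample size, and session frequency is already logged. All of that is correct and limits the consequence. Logged sessions give volume, however, and without minutes per session they do not give time.

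**Conclusion.** The concern holds as an undefined comparator. The Costs row counts time beyond the daily routine without saying whether that routine excludes or includes Asthma Link, and the programme description makes the second reading reasonable. The likely direction of error is downward, and answers may not be comparable between respondents.

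The size cannot be established from the documents. The illustration of 1.5 to 15 nurse-hours per child (54 to 540 h for 36 children) against 0 rests on assumed school days and assumed minutes per session.

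Two stronger statements should not be made. One is that nurse dosing is the main recurring cost: the documents do not rank costs, and family trips and practice time may also recur. The other is that the plan gives a per-session time: the figure of under 5 minutes has no stated unit. No monetary figure is offered, because the documents give no wage rate.

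This should be settled before cost data are collected, since understated answers cannot be corrected afterwards.

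**What to change.** 1. In the Costs row of section 10, and in the survey items if they carry the same qualifier, define the comparator as the routine without Asthma Link. Suggested wording: *time and cost of tasks that would not have been done for this child without Asthma Link, whether or not they have since become routine.*
2. In the school nurse survey, ask for minutes per supervised session. Multiply by the number of sessions logged for that child on the School Nurse checklist to obtain delivery hours per child.
3. Report separately whether that time was absorbed within the working day. This preserves the information that the present qualifier may have been meant to capture, without letting it reduce the cost.

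The cost is slight rewording of survey items and one multiplication using data already being collected. No new data stream is needed. The downside for the programme is a higher reported cost than reading B would give.

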11. PROCEDURES INVOLVED*

Randomization. Two groups of two practices (4 practices in total) will be matched based on comparable size and percent of minority patients. Within each pair, practices will be randomly allocated to Asthma Link or the comparison condition, using a computerized function. This will result in two practices randomized to the Asthma Link condition and two practices randomized to the Enhanced Usual Care comparison condition.

Recruitment will be performed from each practice site until the target n=72 parent-child dyads (18 per site) are recruited. (see section 13 on “Sample size calculation”) Recruitment will begin during the 2021-2022 academic school year.

Procedure Steps:

1. Research coordinator (RC) identifies potentially eligible patients (children aged 6-17 years (enrolled in grade 1-12) years and prescribed a daily inhaled corticosteroid per medical record from most recent visit scheduled for a clinic visit) through the practice's office scheduling and medical record system (e.g., Epic). RC will also collect that patient's name, DOB, mailing and email addresses, phone number, insurance type (as a proxy for socioeconomic status), list of

INVESTIGATOR STUDY PLAN

medications, number of emergency room visits, number of hospital admissions and number of oral steroid courses for asthma relief.

2. RC creates a Lilac Form for any potentially eligible patients as described above. (Lilac form is an indicator to the medical provider seeing the patient that this patient is potentially eligible for study.)

3. Asthma Link condition: As part of clinical practice, medical provider will determine if patient is struggling with taking daily asthma medicine. If YES, then will introduce Asthma Link by saying “There is a clinical program that allows for your child to receive their daily asthma medicine at school supervised by the school nurse.” Child can be enrolled in Asthma Link per the usual clinical steps (see Asthma Link steps).

- After they are enrolled in Asthma Link, medical provider will give family one-page description of study (see Flyer) and state “Researchers at UMass are performing a study of children who are participating in Asthma Link, would you be interested in hearing more?”

3a. Enhanced Usual Care comparison condition: Medical provider will determine if patient is struggling with taking daily asthma medicine, if YES, the provider will give family a one-page description of study (see Flyer) and state “Researchers at UMass are performing a study of children with asthma to learn about how to support them in taking their every day asthma medicine, would you be interested in hearing more?”

- Attached to the “Flyer” will be the Authorization to Contact form. (see Authorization to Contact form)
- If the parent agrees, the Lilac form with the family’s information is faxed to the Research Coordinator. The pediatric office will fax this form with a confidential cover form.
- The fact sheet will be mailed to the parent with a letter saying that the Research Coordinator will call or text them (see Fact Sheet).
- The Research Coordinator will only call the parent five times. The first and third time a message will not be left, but a text message will be sent stating “This is X from Asthma Link, can I call you at TIME?” The second, fourth, and fifth time a message will be left saying “This is X from the University of Massachusetts Medical School. I am calling about the material on Asthma Link I sent you. Please call me back at X.”
- A phone screen will be conducted to ensure study inclusion criteria (see phone script).
- The Research Coordinator will obtain informed consent from eligible participants, including parental permission for their child to participate, child assent to participate, and parental consent to participate. (see sections 30, 31 on Consent)
- After all questions are answered regarding the study by the parent, the Research Coordinator will send the baseline survey via email to the participant to be completed by the parent and child together or will complete the survey over the phone with the child and parent.
- The Research Coordinator will then access the child’s medical record and obtain the discharge summaries, the emergency service records, the office/clinic notes, the problem list, the pulmonary studies, the child’s list of medications, and the child’s height and weight (to help interpret the spirometry data).
- The Research Coordinator will then call the child’s pharmacy to obtain refill history for their daily ICS inhaler.

INVESTIGATOR STUDY PLAN

We anticipate that recruitment of n=72 dyads will take 18 months based on [name] FITLINE study ¹⁸. We do not anticipate issues with this recruitment based on prior recruitment of families for Asthma Link™ from the Worcester community in our pre/post study and based on prior recruitment from these same pediatric practices in the FITLINE study. (also see page 19 which describes estimated number of asthmatics in proposed Pediatric practices, demonstrating feasibility of recruitment). The Institutional Review Board will review all research procedures and protocols. All instruments will be submitted to the IRB for review and approval prior to use.

We will not enroll any participants in the study prior to receiving IRB approval.

SURVEY – PARENT AND CHILD – 20 MINUTES _See uploaded parent baseline, parent 3 month, parent 6 month, and parent 12 month surveys.

The 4 parent surveys will include the following constructs: Patient Health Outcome questions including the Asthma Control Test (ACT; measure of severity of asthma symptoms) and the Maximum Asthma Symptom Days (MSD), Emergency Department visits, hospital admissions, school absences, oral steroid usage and pharmacy refill data. The Baseline survey will include demographic questions that ask about the parent's age, sex, race/ethnicity, relation to the child participating in the study, education, marital status, tobacco usage, health insurance, contact information, family functioning, comorbidities, income, and average monthly as a proxy for socioeconomic status. The 3 month, 6 month, and 12 month follow up surveys for the Asthma Link™ condition will also include the following constructs: acceptability, cost, and sustainability. All surveys will be completed either on-line using RedCap (Please see data management) or over the phone with the Research Coordinator. We are using emails and/or phone calls to deliver/collect these surveys. As soon as the baseline survey has been completed, those completing the survey via email will be automatically sent out future surveys.

SURVEY – SCHOOL NURSE – 10 MINUTES _See uploaded school nurse baseline and end-of-intervention surveys.

The school nurse survey will include the following constructs: acceptability, cost, and sustainability. All surveys will be completed either on-line using RedCap (Please see data management section) or over the phone with the research coordinator. We are using emails and/or phone calls to deliver and collect these surveys.

SURVEY – MEDICAL PROVIDER – 5 MINUTES _See uploaded medical provider baseline and end-of-intervention surveys. The medical provider survey will include the following constructs: acceptability, cost, and sustainability. All surveys will be completed either on-line using RedCap (please see data management section) or over the phone with the research coordinator. We are using emails and/or phone calls to deliver and collect these surveys.

SURVEY- ASTHMA CHAMPION- 5 MINUTES _See uploaded asthma champion baseline and end-of-intervention surveys. This will include the same constructs of acceptability, cost and sustainability. Surveys will be completed either on-line using RedCap (please see data management section) or over the phone with the research coordinator. We are using emails and/or phone calls to deliver and collect these surveys.

INVESTIGATOR STUDY PLAN

We will be accessing the practice's medical record system (same system as above, e.g., Epic) to obtain documentation of the child's emergency room visits, hospital admissions, and oral steroid courses at the baseline time point (recording the number of events for the 6 months prior), 3 month, 6 month, and 12 month time points (recording the number of each of these events for the 3 or 6 months prior.). This data will also be collected 12 months following the completion of the 12 month survey in order to observe for sustained impact on health outcomes and to see if engagement in Asthma Link continues beyond one year. This data will be directly put into the RedCap database without any downloading of information. (please see data management section)

We will be contacting the child's pharmacy to obtain refill history of their daily ICS medication at baseline (obtaining the number of refills for the prior 6 months), 3, 6, and 12 months, and 12 months following the completion of the 12 month survey to assess for medication adherence. This data will be entered directly into the REDCap database.

Portable Spirometry: At baseline, 3, 6, and 12 months the child will perform spirometry in the school nurse's office. The Research Coordinator will perform portable spirometry in the school at the time that the student normally reports to the nurse for their daily asthma medication so as not to disrupt the child's school activities. Given that the spirometry test takes less than 3 minutes to complete for each child, we are confident that it will not pose a disruption to the child's school activities. The Research Coordinator will enter the spirometry data into RedCap for each participant without downloading any data.

School absence data will be collected through school nurse report and will be recorded from the school nurse on the School Nurse checklist and faxed to the Research Coordinator.

Asthma Link Condition: Those practices that are randomized to the Asthma Link group will receive pediatric pulmonologist delivered trainings for pediatric practices on behavioral strategies to help promote asthma medication adherence and a 1 hour training on the Asthma Link clinical program and how to enroll children in Asthma Link (reviewing the steps of this clinical program- see "Asthma Link Clinical Program Steps") and carry out this evidenced-based program in the context of their clinical practice (reviewing the steps to Asthma Link and answering any questions they may have).

Comparison Condition: Those practices that are randomized to the Enhanced Usual Care Comparison Group will receive pediatric pulmonologist delivered trainings for pediatric practices on behavioral strategies to help promote asthma medication adherence. These include training to counsel patients on the strategies such as the placement of cell phone alarms to remember to take their daily medicine and placement of an elastic band around the inhaler and the toothbrush so that a child always remembers to take their daily inhaler before brushing their teeth. We thought it ethically important to provide more than just usual care to the 2 pediatric practices assigned to the comparison condition.

Families who agree to participate in the study from either the Asthma Link or Enhanced Usual Care practices will receive a mailed "Asthma Workbook" to aid in their understanding of asthma, support their asthma care and help with daily medicine adherence (See Asthma Workbook)

INVESTIGATOR STUDY PLAN

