5. BACKGROUND*

Countless pediatric asthma interventions have been successful in improving asthma outcomes in research settings, yet few are adopted into clinical practice to produce noticeable public health impact. Despite aggressive efforts to address remediable causes, childhood asthma still affects 12-15% of children in the urban United States, causes over 14 million missed school days annually and costs billions of dollars in healthcare expenditures.¹⁻³ Most of childhood asthma morbidity is attributable to non-adherence to a daily preventive medication, an inhaled corticosteroid (ICS).⁴⁻⁷ The highest asthma morbidity and the lowest ICS medication adherence rates occur in low income and minority children.⁸⁻¹⁰ These populations fall through the cracks as a result of failure to supervise and support adherence to preventive ICS medication. Recognizing this, the National Asthma Education and Prevention Program and the American Academy of Asthma, Allergy, and Immunology have urged that providers and researchers develop more effective adherence programs.^{11,12}

INVESTIGATOR STUDY PLAN

School-supervised administration of asthma therapy has helped improve medication adherence and improves asthma symptoms among children enrolled in research studies. There have been multiple studies that have shown that school-supervised asthma therapy not only improves medication adherence in children with asthma but also that this practice is safe, with no adverse effects seen.¹³⁻¹⁵ School-supervised asthma therapy has been established as safe and efficacious, and therefore asthma experts (including the American Academy of Pediatrics, American Academy of Allergy Asthma and Immunology, and the National Association of School Nurses) endorse school-supervised asthma therapy as the evidenced-based standard of care.¹⁶

However, despite the compelling evidence from studies and endorsement from experts, these tested school-supervised asthma interventions have not been widely adopted in practice. This is likely due to reliance on research staff for implementation and operations that are costly and highly resource intense, making them infeasible to adopt and sustain in the real world after research funding ends.

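### Two practice-side uptake measures are taken with research case-finding, and the cost surveys leave that work out, so they do not show uptake or cost without research staff

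*Combined protocol and SAP*

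**What the plan says.** Section 5 attributes the poor uptake of earlier school-supervised models to research dependence: "This is likely due to reliance on research staff for implementation and operations that are costly and highly resource intense". It presents Asthma Link as the alternative, to be delivered by pediatricians, school nurses and families "within their current routines and relying on minimal resources and no research staff". On who finds the children it is specific: "Pediatricians identify and enroll children with poorly controlled asthma and medication non-adherence as part of their routine practice". Section 4 makes the case for scaling up, in real-world rather than research settings, conditional on acceptability and on appropriate adoption and sustainability.

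The Procedure Steps in Section 11 start differently. Step 1: "Research coordinator (RC) identifies potentially eligible patients", using the practice's schedule and medical record, on age or grade, a daily inhaled corticosteroid prescription and an upcoming visit. Step 2: "RC creates a Lilac Form for any potentially eligible patients as described above". The form's purpose is stated: "Lilac form is an indicator to the medical provider seeing the patient that this patient is potentially eligible for study". Only in step 3 does the Asthma Link provider ask about adherence, introduce the programme and enrol the child. The study is mentioned after that.

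Two measures in the Section 10 table sit directly downstream. Under fidelity: "Checklist for pediatric practice staff to assess % of eligible children enrolled". Under adoption: "Pedi practice log to track number of providers offering Asthma Link". The cost row covers time and expense for the practice, the school nurse and the family. It does not list coordinator time.

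**The concern.** The prompt that starts identification in the trial comes from research staff, whereas the programme is described as one in which the practice does this itself. The prompt cannot be set aside as a study-only step. In the Asthma Link arm, enrolment in the programme is a study inclusion criterion (Section 6) and precedes any mention of the study, so a flagged child can become a participant only if the provider first offers and enrols the child in the programme. The form therefore acts ahead of the provider behaviour that the two measures record.

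What is at stake is what the pilot can say about uptake. Intervention fidelity is a primary trial outcome in Section 4, and adoption feeds the scale-up argument. If the two figures are read as uptake in routine practice, the planners of the larger trial, or a practice considering the programme, may expect more children to be found, or less effort to find them, than would be the case without a coordinator.

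**Working it through.** The plan gives no figure for the effect of the form, so there is none to reproduce. The check is to trace each measure against the point at which the form enters, then to show ranges under stated assumptions.

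**1. Sequence in the Asthma Link arm (Section 11).** Coordinator search → Lilac form to provider → provider judges adherence → programme offered and enrolled → study mentioned → referral and consent.

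**2. Measures against that sequence (Section 10).**

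| Measure | Directly downstream of the form? |
|---|---|
| Fidelity: share of eligible children enrolled | Yes |
| Fidelity: enrolled students receiving supervised therapy | No, taken after enrolment |
| Fidelity: attendance at nurse sessions and medicine brought in | No, taken after enrolment |
| Adoption: count of providers offering | Yes |
| Adoption: frequency of nurse visits | No, taken after enrolment |
| Adoption: family bringing medicine | No, taken after enrolment |
| Adoption: family obtaining two inhalers | No, taken after enrolment |
| Cost: practice, nurse and family | Coordinator's search not listed |

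One of three fidelity measures and one of four adoption measures are exposed.

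**3. Possible size for the share enrolled (assumed inputs).** Let the observed share be 60%, and let the form multiply uptake by r. Unprompted share = 60% / r.

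- r = 1.0: 60%
- r = 1.25: 48%
- r = 1.5: 40%
- r = 2.0: 30%

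The first line is no effect at all. The listed measures cannot tell which line applies. This illustration concerns the fidelity percentage. The adoption measure is a count of providers (Section 25 allows up to 16 in the study), and the percentages do not carry over to it.

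**4. Possible size of the uncosted search (assumed inputs).** Section 24 gives 7,462 children and an assumed 15% with asthma symptoms: 7,462 × 0.15 = 1,119.3, which agrees with its figure of 1,119. Assume that half belong to the two Asthma Link practices (1,119.3 / 2 ≈ 560) and that each is screened once, at m minutes. Hours = 559.65 × m / 60.

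- m = 2: 18.7 hours
- m = 5: 46.6 hours
- m = 10: 93.3 hours

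Spread over the 36 dyads planned per condition (559.65 × m / 36), this is about 31, 78 and 155 minutes per dyad. The base is rough: it counts grades 1-6 and all children with asthma symptoms, whereas the coordinator screens grades 1-12 for a daily prescription, and screening may stop before the pool is exhausted.

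**5. The two directions are partly alternatives.** Without the coordinator, either the practice takes on the search, and cost rises, or it does not, and fewer children are found. The full effect on uptake and the full effect on cost should not be added together.

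**The case against.** The strongest reply is that the coordinator's search is study recruitment. It is done in both arms, under a HIPAA waiver requested to identify potential subjects (Section 27), and common case-finding is a sound choice when participants are recruited after practices have been randomised. Leaving recruitment effort out of programme cost is also defensible, since the surveys cover the parties who would run the programme. Section 4 frames the study as a pilot of feasibility, not as a test of operation without research staff; that phrase in Section 5 is a goal of the programme.

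Much of this stands. The form should stay, and its use in both arms means that this is mainly a question of generalisability. But the reply does not separate recruitment from programme delivery in the Asthma Link arm, where the same form precedes the programme offer, and Section 4 still rests scale-up on adoption.

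Three further limits stand. The coordinator flags potentially eligible children; the provider still judges adherence. Intervention practices also have prompts of their own, namely exam-room flyers and possible triage-nurse reminders (Section 24). The practice checklist and the programme steps are separate uploads: if the checklist already records how each offer arose, only a reporting commitment is missing.

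A route field also has a limit. If nearly every eligible child has a form, the field will discriminate poorly, and the presence of a form does not prove that it caused the offer. It is still informative for children who enter by the other routes.

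**Conclusion.** The concern holds as a limit on interpretation. The share of eligible children enrolled and the count of providers offering are obtained with research case-finding, and the effort behind that case-finding is outside the listed cost scope. Uptake and cost taken together are likely too favourable as a guide to practice without research staff. The amount is unknown and could be zero; the ranges above rest on assumed inputs.

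A reader might go further in several ways that the documents do not support:

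- *Uptake is overstated and cost understated.* These are likely directions, not demonstrated ones, and they are partly alternatives.
- *Adoption and fidelity are compromised as a whole, or high adoption would be due entirely to the form.* The other five measures are taken after enrolment and are not directly inflated, and other routes to an offer exist.
- *The comparison between arms is biased.* The form is used in both arms, and nothing here bears directly on that comparison.

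This is an inexpensive improvement to a pilot that is meant to inform a larger trial. It is best made before recruitment proceeds, because the route of an offer cannot be reliably reconstructed later.

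**What to change.** 1. Add one field to the practice log for each Asthma Link offer or enrolment: followed a Lilac form, or arose from the flyer, the triage nurse or the provider alone. Report the two practice-side measures by route.
2. Log the coordinator's pre-visit screening time in the Asthma Link practices, and report programme cost with and without it.
3. Describe the two measures as obtained with research case-finding, and do not present them as uptake without research staff.

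If the log continues after Lilac forms stop at a site, those entries may be reported descriptively. They should not be called the real-world adoption estimate: recruitment is expected to take 18 months, so those practices will have worked with the forms for a long period, and there are only two of them.

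The cost is one log field and a time log for existing staff; recruitment is unchanged. The downside for the sponsor is a likely less favourable figure for uptake or for cost.
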